1.4 OBJECTIVES

There is no evidence of release of substances of particular concern, or endocrine disruptors released from Michigan type acrylic occlusal splints.

General objectives: To describe and quantify the values of substances of very high concern (SVHC) or endocrine disruptors (ED) released from printed or injected acrylic Michigan type splints.

Specific objectives:

1. To identify the SEPs and EDs released by Michigan-type splints made by injection or *in vitro* impression technique, simulating oral environment and wear.
2. Identify SEPs and EDs in saliva released from printed or saliva-injected acrylic Michigan type splints before, during and after insertion in the mouth.
3. To quantify the levels of SEP and ED in saliva released from printed or injected acrylic Michigan type splints in saliva before, during and after insertion in the mouth.
4. Contrast the results obtained in the laboratory test with those recorded in the saliva samples of the *in vivo* study.

5. Relate the results to the manufacturing process, stage of exposure, time, habits and individual characteristics of each volunteer.

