2 METHODOLOGY OF THE STUDY

2.1 DESIGN

This is a prospective analytical observational experimental pilot study that aims to analyse the substances of particular concern and endocrine disruptors detected in saliva, released by conventional dental devices, before and after the intervention. They will therefore be paired samples, where the control group will be the same subject, minimising the independent variables: saliva pH, microbiome, salivary flow, habits, occlusal wear, erosion by external agents and saliva.

Saliva sampling shall be carried out in accordance with the conventional protocol RD 1716/2011. The saliva containers shall comply with the requirements of the ISO 6717:2021 standard. They shall be packaged and transported according to the protocol Order JUS/1291/2010 of 13 May. All samples shall be identified with the number assigned to the volunteer, time, material and type of manufacture (processed, machined or printed), and shall be sent to the Chemical Institute for Energy and Environment (IQUEMA). University of Cordoba, where they will be analysed by the SAC group, for subsequent statistical treatment and interpretation.

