2.3.4 STATISTICAL DATA CONTROLLER

[name] [name] (Methodological and Statistical Advisory Group, Department of Medicine, Faculty of Biomedical and Health Sciences), European University of Madrid.

2.4 POPULATION AND CALCULATION OF THE SAMPLE.

The sample will be obtained from patients who are registered in the database of the Polyclinic of the European University of Madrid, who request a Michigan type splint for the treatment of bruxism, made of acrylic, made in two of the usual ways: printed or injected, in accordance with the inclusion and exclusion criteria shown in Appendix I. As the samples were treated with an innovative methodology in the field of dentistry, such as super solvents, this was a pilot study in which two groups of 15 participants each were formed, depending on the manufacturing process of the splint: injected or printed, totaling 30 volunteers.

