2.6 DESCRIPTION OF THE STUDY

2.6.1 VOLUNTEER RECRUITMENT:

The study groups will be formed in accordance with the requirements and inclusion criteria. Each of the subjects will be informed of the purpose and methodology of the project by means of an information document for the volunteer (Appendix II) and must sign the informed consent form provided for this purpose (Appendix III); they may withdraw from participation at any time. The data of the participants will be stored in a clinical history with an individual key number, in accordance with the regulations contained in the current Organic Law 3/2018, of 5 December, on the Protection of Personal Data.

Appointments will be made as follows:

APPOINTMENT 1: A conventional computerised clinical history is taken of the patient, in which data is collected on general health, orofacial and nutritional habits and hygiene. We explain in detail what the treatment consists of: Michigan type relaxation splint (device to prevent tooth wear due to bruxism). Each intervention is governed by scientific and deontological criteria, respecting all the ethical rules of research. The following is a detailed description of the study, its duration and methodology. The four moments of saliva collection will be explained: before, during, and 3 and 6 months after placement, as follows:

-Time 0: the day of the appointment, before the intervention.

-Step 1: On the day of the appointment, device placement.

-Time 2: 3 months after device placement.

-Time 3: 6 months after treatment.

Information and informed consent will be provided.

APPOINTMENT 2: Preparation and taking of models for the Michigan type splint according to the conventional protocol for this treatment.

APPOINTMENT 3: The models will be assembled in the articulator to send and request the making of the splint, specifying whether it is injected or printed.

APPOINTMENT 4: A saliva sample is taken in the device for this purpose. After checking for proper fit and retention, the occlusal adjustments will be made with a handpiece and conventional acrylic and polishing burs. After completion of the procedure, a new saliva sample shall be taken. The samples shall be identified with the patient's assigned code and stored according to conventional standards. An appointment will be made after 6 months to continue with the study and in accordance with the check-up times for correct oral health.

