2.8 STATISTICAL ANALYSIS

For the descriptive analysis of the variables collected, the mean \pm standard deviation or median [interquartile range] will be used once the distribution has been checked, in the case of the variables collected.

RESEARCH PROTOCOL

quantitative variables. To describe qualitative variables, absolute (n) and relative (%) frequencies will be used and their 95% confidence interval (95% CI) will be calculated.

Chi-square tests (or Fisher's exact tests) will be used to study differences between qualitative variables. In case of quantitative variables, Student's t-test or Man-Whitney U-test will be used, depending on whether they follow parametric or non-parametric behaviour. Binary logistic regression models will be used to determine the Odds ratio (OR) of seroprevalence and its 95% confidence interval (95% CI) to analyse the effect of each variable on the results obtained.

All statistical calculations were performed using SPSS statistical software (version 25.0 IBM Corp.; USA). Statistically significant differences were assumed to exist if the p-value obtained was less than or equal to 0.05.

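### The saliva data are defined as paired, but the rank and categorical tests named in Section 2.8 are for independent groups and no paired or repeated-measures method is given

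*Protocol*

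**What the plan says.** Protocol Section 2.1 fixes the structure of the data: "They will therefore be paired samples, where the control group will be the same subject". Section 2.6.1 sets the sampling: "The four moments of saliva collection will be explained: before, during, and 3 and 6 months after placement". These are Times 0, 1, 2 and 3, and Annex IV has one concentration column for each. In Section 1.4, specific objectives 2 and 3 concern substances "in saliva before, during and after insertion in the mouth", and objective 5 relates the results to exposure stage and time, among other factors. Section 2.4 gives the sample: "two groups of 15 participants each were formed, depending on the manufacturing process of the splint: injected or printed, totaling 30 volunteers".

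Section 2.8 then names the tests. For quantitative variables: "Student's t-test or Man-Whitney U-test will be used, depending on whether they follow parametric or non-parametric behaviour". For categorical variables: "Chi-square tests (or Fisher's exact tests) will be used to study differences between qualitative variables". It adds binary logistic regression with no term for the participant, and a significance threshold of p ≤ 0.05. It does not say which test serves which comparison. No other part of the protocol names a paired or repeated-measures method.

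**The concern.** There is no untreated group, so release into saliva can only be shown by comparing a person's later samples with that person's Time 0 sample. That comparison defines the design, and the listed tests do not fit it. Mann-Whitney, chi-square and Fisher treat the before and after values as coming from different people. A logistic model fitted to several samples per person without a subject term does the same. Student's t-test has a paired form, but the usual rank alternative to that form is Wilcoxon signed-rank, not Mann-Whitney.

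Unpaired tests on paired data have the wrong error rate. With positive within-person correlation they reject too rarely. Section 1.4 opens with the proposition that there is no evidence of release, so a lost signal would be read as support for it. The study would also give up the main advantage of using each person as their own control, with only 30 people.

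**Working it through.** **Inputs from the protocol.** Two groups of 15, and 2 × 15 = 30 as stated (Section 2.4). Four samples per person (Section 2.6.1, Annex IV). Threshold p ≤ 0.05 (Section 2.8), taken as two-sided because sidedness is not stated. No power, SD, effect size or correlation is given, so there is no power figure to reproduce.

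**Assumptions for illustration.** Normal before and after values with the same SD, a shift of 0.5 SD, and within-person correlation ρ varied.

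**Why pairing matters.** For n pairs, the mean change has variance 2σ²(1 − ρ)/n. The independent t-test uses 2σ²/n whatever ρ is, so its standard error is too large when ρ > 0 and too small when ρ < 0.

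**Paired t, n = 30.** Noncentrality = 0.5 × √30 / √(2(1 − ρ)) = 2.739 / √(2(1 − ρ)), with 29 degrees of freedom:

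- ρ = 0: 1.936, power 46.5%
- ρ = 0.3: 2.315, power 60.9%
- ρ = 0.5: 2.739, power 75.4%
- ρ = 0.7: 3.536, power 92.7%
- ρ = 0.8: 4.330, power 98.7%

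**Independent t on the same data.** The statistic is centred near 0.5 / √(2/30) = 1.936 at every ρ, against a critical value of 2.002 (58 degrees of freedom). Power therefore stays just under one half. Under no shift, the spread of the statistic shrinks by about √(1 − ρ), which drives the type I error down. Simulation (50,000 trials per setting for the t-tests, 20,000 for the rank tests), n = 30:

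| ρ | Independent t power | Paired t power | Type I error, independent t | Mann-Whitney power | Signed-rank power |
|---|---|---|---|---|---|
| 0 | 48% | 46% | about 5% | 45% | 45% |
| 0.3 | 48% | 61% | 2.0% | 45% | 59% |
| 0.5 | 47% | 75% | 0.7% | 45% | 73% |
| 0.7 | 46–47% | 93% | about 0.1% | 44% | 92% |
| 0.8 | 46% | 99% | about 0.01% or less | 44% | 98% |

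At ρ = −0.2 the type I error of the independent t-test is about 7%. The paired t-test stays near 5% throughout.

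**Within one manufacturing group, n = 15.** Power of independent versus paired t: 26% vs 25% (ρ = 0), 23% vs 33% (0.3), about 20% vs 44% (0.5), 15% vs 64% (0.7).

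**Detected / not detected.** Suppose 12/30 are positive before and 18/30 after (assumed counts). Fisher gives p = 0.20 and uncorrected chi-square p = 0.12, whichever people changed. Exact McNemar uses only those who changed, by a binomial with probability 0.5:

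| Convert / revert | Exact McNemar p |
|---|---|
| 6 / 0 | 0.031 |
| 7 / 1 | 0.070 |
| 8 / 2 | 0.109 |
| 9 / 3 | 0.146 |
| 12 / 6 | 0.238 |

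The same margins can thus fall on either side of 0.05, depending on information that the named tests ignore.

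**The case against.** **The t-test may be meant as paired.** Section 2.8 does not exclude this, and a paired t-test would be valid for two time points. That much stands. It leaves skewed concentrations and detection data without a valid before/after test.

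**The tests may be meant only for injected versus printed.** They are correct there, and Section 2.8 assigns no test to before/after. On that reading the comparison that defines the design has no stated method, so Section 2.8 still needs correcting. Nor is this only detail left to an analysis plan, because the protocol does fix a list of tests and the list does not match Section 2.1.

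**The objectives are largely descriptive and this is a pilot.** Objectives 2 and 3 are to identify and quantify, and descriptive summaries by time are unaffected. But Section 2.8 sets a significance threshold, and objective 5 asks for results to be related to stage and time. The opening sentence of Section 1.4 is not labelled a hypothesis, though reading it as one is fair.

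**The size depends on the scenario.** This stands. If the baseline SD is one tenth of the later SD (ρ = 0.5, n = 30, shift 0.5 of the later SD), power is 77% for independent and 79% for paired t, and the type I error of the independent test is about 4.5%. With 0/30 detected before and 6/30 after, Fisher gives p = 0.024 and exact McNemar 0.031. The loss can be small for a substance almost absent at baseline. Section 1.2 notes that these additives are common in the surroundings, so appreciable background is plausible for some compounds.

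**The error is conservative.** This is true only when the correlation is positive. In a study of exposure, failing to see release is the more troublesome error.

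**Conclusion.** The concern holds: Section 2.8 is wrong as written for comparisons of Times 1, 2 and 3 with Time 0. The mismatch with Section 2.1 follows from the text and needs no assumption.

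Its size does rest on assumptions. With equal variances, a 0.5 SD shift and a correlation of 0.5, unpaired testing cuts power from about 75% to 47% at n = 30 and from 44% to about 20% at n = 15. At zero correlation there is no loss, and at negative correlation the unpaired tests reject too often. The protocol gives no correlation, variance or effect size. However, its reason for using the same subject as control, to limit the influence of salivary and personal factors, presumes positive correlation.

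Between-group tests on one value per person and descriptive results are not affected. The point should be corrected before analysis, because it determines the before/after p-values and the conclusions drawn from them.

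**What to change.** Necessary, in Section 2.8:

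- **Concentrations, Times 1, 2 and 3 against Time 0:** paired t-test or Wilcoxon signed-rank, or a mixed model with a random participant effect covering all four times.
- **Detected / not detected:** exact McNemar for each comparison with Time 0. Cochran's Q may be added as an overall test across the four times, but it does not replace those comparisons.
- **Existing tests:** state that Student's t (independent form) or Mann-Whitney, and chi-square or Fisher, are for comparisons between people, such as injected versus printed, with one value per person.
- **Logistic regression:** restrict it to one observation per person, or include a within-person term.

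Optional: compare injected with printed on change from Time 0, or adjust for the Time 0 value, which is already collected.

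The cost is a change of wording. Annex IV already records all four concentrations by volunteer, so no further participants, samples or visits are needed.

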APPOINTMENT 5: The intraoral check-up will be carried out, checking the intraoral health and the state of the splint, with the pertinent adjustments, according to conventional protocol. A new saliva sample will be taken. The patient will be seen after 3 months.

APPOINTMENT 6: The intraoral check-up will be carried out, checking the intraoral and splint health status, with its pertinent adjustments, according to conventional protocol. A new saliva sample will be taken. The sample collection period for this subject will end.

Prior to this, the substances released by the specific material used to make the devices will be identified in the laboratory. The reason for this is the highly dynamic nature of the dental materials market. For this purpose, the solutions will be analysed by liquid chromatography coupled to a mass spectrometer (LC-HRMS). The identification of the compounds present will be based on a non-directed suspect screening approach, comparing the results obtained in the analyses with those already existing for the

RESEARCH PROTOCOL

compounds included in the

list of suspects. This list shall be compiled on the basis of information gathered during the literature review, among other sources. Thus, it shall include from compounds whose presence is expected such as those indicated by the manufacturer, to emerging compounds that could be present due to storage conditions, use, etc. For the identification, statistical and chemometric techniques will be used to establish the correlation between the analytical signals obtained in the LC-HRMS and the information (e.g. masses, structure, mass spectra, etc.) available in bibliography and publicly available spectrophotometric libraries (e.g. Mass Bank). In a second phase, the compounds identified in the first stage will be prioritised according to their level of identification, frequency of detection, toxicity (if known) and availability of analytical standards. Finally, quantification of these compounds will be carried out (figure 1).

[figure not shown]

Figure 1: Timeline *In vitro* study of acrylic-based dental materials: Resting and weathering phase leaching, identification and quantification of released substances EDs and SEP. SAC innovative research group at the University of Córdoba (Spain) that belongs to the Institute of Fine Chemistry and Nanochemistry (IUNAN).

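### Section 2.8's only regression models the odds of seroprevalence, which this saliva study does not measure, and the section names no paired rank or categorical test for a design declared paired

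*Protocol*

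**What the plan says.** **Regression.** Protocol Section 2.8 states: "Binary logistic regression models will be used to determine the Odds ratio (OR) of seroprevalence", with a 95% confidence interval. The sentence goes on to say that the purpose is to examine how each variable affects the results. No other regression is named.

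**Tests.** For quantitative variables, "Student's t-test or Man-Whitney U-test will be used, depending on whether they follow parametric or non-parametric behaviour". For qualitative variables, chi-square or Fisher's exact tests "will be used to study differences between qualitative variables". The section does not say which test serves which comparison. The significance threshold is 0.05.

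**Design.** Section 2.1 says of the saliva samples: "They will therefore be paired samples, where the control group will be the same subject". The reason given is "minimising the independent variables: saliva pH, microbiome, salivary flow, habits" and other personal factors. Section 2.6.1 sets the schedule: "The four moments of saliva collection will be explained: before, during, and 3 and 6 months after placement". Annex IV has one concentration column for each of the four samples. Section 2.6 lists the dependent variables as substances of very high concern and endocrine disruptors. Section 2.4 forms two groups of 15, injected and printed.

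**The concern.** There are two problems, and the first is the firmer.

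1. The regression outcome matches nothing in the study. Specific objective 5 (Section 1.4) relates the results to manufacture, time, habits and personal characteristics, and this regression is the only model named for that kind of question. It cannot be run until someone chooses another outcome. If that choice is made after the data are seen, the odds ratios lose most of their value.

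2. The design relies on comparing each volunteer with himself or herself, but the rank and categorical tests named assume independent samples. If they are used for before/after comparisons, the pairing is discarded and real release is easier to miss. If all four samples per volunteer are pooled to compare splint types, the error runs the other way, because repeated samples from one person are counted as separate people.

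**Working it through.** The protocol gives no effect size, standard deviation, correlation or power, and sets 30 as a pilot size, so it has no figure of its own to reproduce. Step 1 rests on the text. Steps 2 to 5 are illustrations, and every shift, correlation and detection rate in them is an assumption.

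**Step 1. Outcome of the regression.** Section 2.8 models seroprevalence, a word found nowhere else in the protocol. The appointments in Section 2.6.1 collect saliva only. Section 2.6 makes the substances the dependent variables, and Annex IV records concentrations. Detected or not detected is the natural yes/no outcome. Section 2.6 already uses detection frequency in the laboratory phase, where compounds "will be prioritised according to their level of identification, frequency of detection, toxicity (if known) and availability of analytical standards". Section 2.8 does not make that link.

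**Step 2. Before/after concentrations.** Inputs: n = 30 (Section 2.4), two-sided 0.05 (threshold from Section 2.8; two-sided assumed), shift d = 0.5 SD (assumed), within-person correlation r (assumed).

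- Unpaired t: noncentrality d × √(n/2) = 0.5 × √15 = 1.94, 58 df, nominal power 48%.
- Paired t: noncentrality d × √n / √(2(1 − r)), 29 df. At r = 0.5 this is 0.5 × 5.477 / 1 = 2.74, power 75%.

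Simulation gives the rank tests (signed-rank on the log scale):

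| r | Paired t | Mann-Whitney | Signed-rank | Mann-Whitney, actual type I error |
|---|---|---|---|---|
| 0 | 47% | 46% | 46% | 4.8% |
| 0.3 | 61% | 44% | 59% | 1.9% |
| 0.5 | 75% | 43-44% | 73-74% | 0.7% |
| 0.7 | 93% | 43-44% | 92% | 0.1% |

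The signed-rank test keeps its error near 5%. With r = 0 the pairing gains nothing.

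**Step 3. Before/after detection.** Suppose detection rises from 6/30 to 13/30 and nobody changes from detected to not detected. There are then 7 discordant pairs, all in one direction. Exact McNemar p = 2 × 0.5⁷ = 0.016. On the same counts Fisher gives p = 0.095 and uncorrected chi-square p = 0.052. On average the gain is smaller than this example suggests. With detection rising from 30% to 60% and latent correlation 0, 0.3, 0.5 and 0.7, power is:

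- Fisher: 55, 57, 56, 57%
- uncorrected chi-square: 66, 68, 69, 70%
- exact McNemar: 55, 63, 70, 80%

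Exact McNemar therefore passes uncorrected chi-square only from about 0.5. The asymptotic form (about 63, 72, 79, 87%) already does so at 0.3.

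**Step 4. Pooling four samples per volunteer.** If 30 × 4 = 120 rows entered a logistic model of injected versus printed as if independent, the simulated type I error would be about 11, 15, 20 and 24% at latent intraclass correlation 0.23, 0.41, 0.55 and 0.73, against a nominal 5%.

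**Step 5. Choice of the between-group comparison.** For 15 versus 15 and an assumed difference of 1 SD, power at r = 0, 0.3, 0.5 and 0.7 is:

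- one time point, no adjustment: 75% throughout
- change from Time 0: 46, 61, 75, 93%
- adjusted for Time 0 (ANCOVA, simulated): about 73, 78, 86, 95%

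Adjustment costs almost nothing when the correlation is nil and otherwise does better than both alternatives.

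**The case against.** The best defence is that Section 2.8 assigns no test to any comparison. It nowhere states that Mann-Whitney, chi-square or Fisher will be used before versus after. The study also has an independent-groups comparison, injected versus printed, for which these tests are right, and Student's t includes the paired form. A statistical analysis plan, not shown here, could allocate the tests. This stands in part: the second problem is a missing paired rank and categorical test set against an explicitly paired design, not a stated misuse. A reader might infer that every test in Section 2.8 is wrong, or that concentrations go unanalysed. The text supports neither.

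On the regression, the rest of the sentence points to the study's own results, so seroprevalence looks like a carried-over word. That makes the repair easy but does not remove the error. An analysis plan would have to contradict the sentence, not add detail to it.

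Two further inferences are tempting. One is that the only danger is missed release. That holds for an unpaired before/after test under positive correlation, but pooling repeated samples produces false positives. The other is that low power favours a working hypothesis, because Section 1.4 opens with "There is no evidence of release of substances of particular concern, or endocrine disruptors released from Michigan type acrylic occlusal splints". The next line there sets a descriptive aim, and Sections 1.3 and 2.4 call this a pilot, so the documents do not carry that reading.

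**Conclusion.** The concern holds in two parts of unequal strength. The regression outcome is wrong as written, whatever is assumed about the data. The absence of any paired rank or categorical test is a real mismatch with Section 2.1, but it affects only before/after comparisons of non-normal or yes/no data.

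The size of the power loss depends on a within-person correlation that the documents do not give. It is nil at 0 and large at 0.5 or above (about 43% against 73% at 0.5, for an assumed 0.5 SD shift). The concentration figures also assume that every value is quantified, whereas samples taken before placement may well include non-detects. The point should be fixed. It does not threaten the design or the sample collection.

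**What to change.** Revise Section 2.8 as follows.

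- **(a) Regression.** Replace seroprevalence with detection (yes/no) of each substance in saliva. Fit the model at a stated time point, or by generalised estimating equations with the volunteer as cluster when several samples are used. Keep few covariates and label the models exploratory.
- **(b) Change over time.** Compare each later time with Time 0 within volunteer by the paired t-test or Wilcoxon signed-rank test. Use log concentrations only where values are quantified, or with a stated rule for non-detects. Use McNemar's test for detected/not detected, and say whether it is the exact form.
- **(c) Injected versus printed.** Compare at each later time, adjusted for the Time 0 value (ANCOVA), or by Mann-Whitney U when the data are non-normal. Reserve Mann-Whitney U and chi-square/Fisher for between-group comparisons.

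**Cost.** Rewording and slightly more analysis, with standard procedures and no new samples or visits. Three comparisons with Time 0 per substance carry about a 12-13% chance of at least one false positive (simulated), so estimates with 95% confidence intervals should be reported as exploratory. Generalised estimating equations are slightly liberal with 30 volunteers: simulated type I error is about 5-7% for manufacture and 6-8% for time.

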ANNEX IV

Voluntary code	CONCENTRATIONS	CONCENTRATIONS	CONCENTRATIONS	CONCENTRATIONS
	M. Saliva 0	M. Saliva 1	M. Saliva 2	M. Saliva 3
SUBSTANCES				

 Name, surname, ID number and signature of the researcher _____
Date

Sample collection table for each volunteer

VARIABLES	Volunteer 1	Volunteer 2	Volunteer 3	Volunteer 4	Volunteer 5
AGE	-				
GENDER (MALE, FEMALE, OTHER)					
MATERIAL (ACRYLIC)					
MANUFACTURING (INJECTED or PRINTED)		-			
USUAL RESIDENCE (URBAN, RURAL)			-		
EXPOSURE TIME (HOURS) BRUXIST (YES/NO)				-	
REFLUX (YES/NO)					
ANTIDEPRESSANTS (YES/NO)					
ANTIHISTAMINES (YES/NO)					
DECONGESTANTS (YES/NO)					

BIBLIOGRAPHY

- Alhazzawi, T. F. (2016). Advancements in CAD/CAM technology: Options for practical implementation. *Journal of Prosthodontic Research*, *60*(2), 72-84.
<https://doi.org/10.1016/J.JPOR.2016.01.003>
- Alharbi, H. F., Algonaiman, R., Alduwayghiri, R., Aljutaily, T., Algheshairy, R. M., Almutairi, A. S., Alharbi, R. M., Alfurayh, L. A., Alshahwan, A. A., Alsadun, A. F., & Barakat, H. (2022). Exposure to Bisphenol A Substitutes, Bisphenol S and Bisphenol F, and Its Association with Developing Obesity and Diabetes Mellitus: A Narrative Review. *International Journal of Environmental Research and Public Health*, *19*(23).
<https://doi.org/10.3390/ijerph192315918>
<https://doi.org/10.1016/J.ADDMA.2020.101693>
- Bisphenol A and incisor molar hypomineralisation:: A review - Dialnet* (n.d.). Retrieved June 17, 2023, from <https://dialnet.unirioja.es/servlet/articulo?codigo=7998248>
- Carneiro Pereira, A. L., Bezerra de Medeiros, A. K., de Sousa Santos, K., Oliveira de Almeida, É., Seabra Barbosa, G. A., & da Fonte Porto Carreiro, A. (2021). Accuracy of CAD-CAM systems for removable partial denture framework fabrication: A systematic review. *Journal of Prosthetic Dentistry*, *125*(2), 241-248.
<https://doi.org/10.1016/j.prosdent.2020.01.003>

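### For age and exposure hours, section 2.8 names no method that keeps the saliva concentration uncut: its only model is a binary logistic regression on an undefined seroprevalence outcome

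*Protocol*

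**What the plan says.** Section 2.8 lists chi-square or Fisher tests for qualitative variables, Student's t or Mann-Whitney U for quantitative ones, and one model: "Binary logistic regression models will be used to determine the Odds ratio (OR"), with seroprevalence as the outcome and a 95% confidence interval. The purpose given for that model is "to analyse the effect of each variable on the results obtained". Significance is fixed by the sentence "Statistically significant differences were assumed to exist if the p-value obtained was less than or equal to 0.05".

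The results to be analysed are amounts. Objective 3 in section 1.4 is "To quantify the levels of SEP and ED in saliva", and Annex IV has a concentration field per substance for each of four saliva samples. Objective 5 is to "Relate the results to the manufacturing process, stage of exposure, time, habits and individual characteristics of each volunteer". Among the characteristics collected in Annex IV are age and "EXPOSURE TIME (HOURS"). Section 2.6 also lists age as an independent variable and says that the results will be correlated with age, material, manufacture and habits, without naming a method.

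Section 2.4 sets the size: "two groups of 15 participants each were formed, depending on the manufacturing process of the splint: injected or printed, totaling 30 volunteers".

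**The concern.** A binary logistic model needs a two-level outcome. Section 2.8 gives it one, seroprevalence, which this saliva study does not measure, and defines no other. To use the model for Objective 5, the analyst must first turn each concentration into yes/no: above some cut, or detected. The protocol gives no cut. The limits quoted in section 1.2 are daily intakes per kg of body weight, not saliva concentrations, so they do not supply one.

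At stake is whether the study can say how release varies with age or hours of exposure. After a cut, a value just above it and a very high value count the same. A substance found in nearly everyone leaves almost no variation to explain. The odds ratio also does not say by how much the concentration changes, which is the stated quantity of interest and what a later study would need from this pilot.

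**Working it through.** **Step 1: which named methods reach which covariate, with the concentration left uncut**

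| Covariate | t-test / Mann-Whitney U | Chi-square / Fisher | Binary logistic |
|---|---|---|---|
| Manufacture, residence, yes/no items | Yes | No, outcome cut | No, outcome cut |
| Age, exposure hours | Only if the covariate is split into two groups | No, both cut | No, outcome cut |

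The gap is therefore confined to the covariates recorded on a scale: age and exposure hours.

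**Step 2: inputs for the size**

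From the protocol: n = 30 (section 2.4) and p ≤ 0.05 (section 2.8). It states no effect size, spread, cut or detection rate, and no power figure to reproduce. Assumed: two-sided test, one continuous covariate x, and log concentration y = r·x + √(1 − r²)·e, with x and e standard normal.

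**Step 3: power with the concentration uncut**

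Approximation: power ≈ Φ(atanh(r)·√(n − 3) − 1.96), with √27 = 5.196.

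- r = 0.3: Φ(0.3095 × 5.196 − 1.96) = Φ(−0.35) = 0.36
- r = 0.4: Φ(0.4236 × 5.196 − 1.96) = Φ(0.24) = 0.60
- r = 0.5: Φ(0.5493 × 5.196 − 1.96) = Φ(0.89) = 0.81
- r = 0.6: Φ(0.6931 × 5.196 − 1.96) = Φ(1.64) = 0.95

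The simulated values in step 4 agree with these.

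**Step 4: logistic regression after a median split (3,000 simulated data sets per row)**

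| r | Linear on log concentration | Logistic, Wald | Logistic, likelihood ratio | Loss in points, Wald / likelihood ratio |
|---|---|---|---|---|
| 0.3 | 0.365 | 0.210 | 0.281 | 15.5 / 8.4 |
| 0.4 | 0.613 | 0.368 | 0.466 | 24.5 / 14.7 |
| 0.5 | 0.827 | 0.537 | 0.640 | 29.0 / 18.7 |
| 0.6 | 0.957 | 0.764 | 0.836 | 19.3 / 12.1 |
| 0.7 | 0.997 | 0.918 | 0.954 | 7.9 / 4.3 |

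Over r = 0.3 to 0.6 the loss is about 16 to 29 points (Wald) or 8 to 19 (likelihood ratio). A separate set of runs gave about 18 to 28 and 10 to 18, so the ends of the range are uncertain by a point or two. With r = 0, rejection rates were 0.044 (linear), 0.033 (Wald) and 0.056 (likelihood ratio), so part of the Wald loss is that test's conservatism. A cut that leaves only 20% above it costs more: at r = 0.5, 0.815 against 0.369 (Wald) or 0.508 (likelihood ratio).

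**Step 5: outcome detected/not detected, r = 0.5**

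The comparator is a rank correlation with non-detects tied lowest.

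| Share detected | Rank correlation | Logistic, Wald | Logistic, likelihood ratio |
|---|---|---|---|
| 90% | 0.77 | 0.14 | 0.38 |
| 80% | 0.757 | 0.366 | 0.530 |
| 50% | 0.697 | 0.568 | 0.662 |
| 30% | 0.568 | 0.470 | 0.584 |

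Against the likelihood-ratio test the loss is 39 points at 90% detected (0.77 − 0.38), 3.5 at 50% (0.697 − 0.662) and −1.6 at 30% (0.568 − 0.584). The damage falls on commonly detected substances.

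**The case against.** A reader might infer that section 2.8 forces every concentration to be cut, so that effects of manufacture or habits would be missed as well. The documents do not support that. The t-test and Mann-Whitney U compare uncut concentrations between injected and printed splints, urban and rural residence, and every yes/no item in Annex IV. No loss can be charged to the plan for those factors.

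Detected/not detected is also a proper binary outcome. It suits the identification objective (Objective 2), and a logistic model for it is legitimate. This stands, and is why the model should be narrowed rather than removed.

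It can further be said that section 2.6 plans to correlate results with age, and that the choice of coefficient may be left to a statistical analysis plan not at hand. That would answer a complaint about missing detail. It does not answer this one: section 2.8 does commit to a model for this purpose, and that model cannot use a concentration. Splitting age or hours into two groups for a t-test would keep the concentration, but cuts the covariate instead.

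Last, this is a descriptive pilot of 30 that claims no power, and only two covariates are affected. That limits the weight of the point. It does not make the named model fit the data.

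**Conclusion.** The point holds for age and exposure hours, and not beyond them. For these two, section 2.8 offers only a binary model with an undefined outcome that is foreign to the study, although the concentrations are recorded.

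It is tempting to quote one fixed cost, such as 20 to 30 points of power. The protocol supports no such figure, because effect size, cut, test and detection rate are all unstated. Under the assumptions above, a median split costs roughly 16 to 29 points (Wald) or 8 to 19 (likelihood ratio) at correlations of 0.3 to 0.6, and less for a very strong relation. With a detection outcome, the cost runs from very large at about 90% positive to about nil against the likelihood-ratio test at 30 to 50% positive. The change should be made: it is cheap, and without it Objective 5 has no suitable named analysis for age or hours.

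**What to change.** Amend section 2.8 as follows.

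- **Substances quantified in most samples:** relate concentration to age and exposure hours by regression on log concentration, reporting the ratio of geometric means with 95% CI per unit of the covariate.
- **Where such substances have non-detects:** use a rank correlation with non-detects tied lowest, or a censored regression.
- **Time 0:** take the Time 0 concentration into account in these analyses, because section 2.1 makes each subject their own control.
- **Rarely detected substances:** keep logistic regression for detected/not detected, and replace seroprevalence with that outcome. State in advance the detection share that separates the two routes.
- **Two-level factors:** leave the t-test and Mann-Whitney U as they are.

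The cost is a short rewrite of one paragraph, a check of residuals on the log scale, and two result formats (ratios for common substances, odds ratios for rare ones). Annex IV already provides for the data, so no sample, visit or assay is added.
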